6.2.3 MOTIVATIONAL INTERVIEWING (PROMOTION OF ADHERENCE TO INTERVENTION)

To facilitate adherence to the dietary and behavioral changes above, motivational interviewing (MI) techniques will be employed by the study team. MI is a patient-centered method for enhancing intrinsic motivation to change health behavior by exploring and resolving ambivalence through the use of empathetic, nonjudgmental, and supportive communication techniques (37). Numerous studies have illustrated the efficacy of MI as a promising strategy to encourage positive health behavior change (38), including promoting health behavior change and weight loss in nutrition and exercise interventions in children and adults (37, 39). Specifically, MI has been used to promote diet and exercise in breast cancer patients with some success (41).

6.2.4 INTEGRATION OF INTERVENTION INTO ALL THERAPY

While induction chemotherapy for pediatric ALL is a highly morbid and overwhelming time, the study team has significant experience working both with this specific population as well as other populations with high morbidity. While lifestyle changes in general are difficult to achieve, short-term changes are generally more successful and patients and families in general are more receptive to short-term achievable goals.

In this context, the 28 day intervention proposed here is purposefully designed to naturally integrate into the four week induction phase beginning with the start of systemic chemotherapy. This phase routinely includes an initial hospitalization followed by weekly clinic visits with the treating provider for delivery of chemotherapy and evaluation of toxicity. The study intervention and assessments are therefore formulated around this routine clinical schedule.

Subjects will be enrolled surrounding the time of initial diagnosis within 24 hours of starting systemic chemotherapy. Children are routinely hospitalized for a minimum of four days from the start of systemic chemotherapy. During this time, they will have their baseline DXA scan (within 96 hours from start of systemic chemotherapy), the initial PT and RD assessments, and start with the supervised activity intervention and diet intervention. Bedside nursing will be available to provide reinforcement during that time. Following anticipated discharge, the subjects will be assessed at each weekly clinic visit to have their diet and activity interventions monitored and adjusted as needed and also to receive

education/motivation from the psychosocial team. At the final clinic visit at the end of induction, subjects will receive the post-intervention assessments along with additional motivation/education. Subjects will then continue on chemotherapy per routine care with ~8-9 additional months of intensive chemotherapy; subjects will receive PT, RD, and QOL assessments midway at the start of “interim maintenance” and again at the final time-point at the start of the low-intensity maintenance phase. These follow-up visits will help gauge whether the effect of the intervention and education extinguished or persisted during the intervening post-intervention months.

6.3 SUBJECT REMUNERATION

While no payment is provided to subjects for participation, a Fitbit© will be provided to participants, as part of the study assessments as indicated in the schema and described further below. At the conclusion of the study’s follow-up portion, the subjects (or parent/guardian if the subject is <13 years of age) will be permitted to keep the Fitbit should they wish to do so.

7.0 MODIFICATIONS OF INTERVENTION FOR TOXICITY

7.1 MODIFICATION OF ACTIVITY INTERVENTION

Instances may arise throughout the course of induction therapy in which subjects may not be able to adhere to the prescribed activity intervention due to complications from leukemia treatment. Initially, attempts will be made by the PT to lower the intensity of the intervention until complications subside. If treatment-toxicity is persistent or severe (i.e. subject in the PICU), the activity intervention will be suspended until the subject is deemed to be able to resume the intervention by the PT in consultation with the subject’s treatment team.

7.2 MODIFICATION OF DIETARY INTERVENTION

Similarly, a subject may not be able to adhere to the nutrition intervention for reasons such as, nausea/emasis or the treatment team determining the subject cannot receive liquids or food by mouth (NPO). In such instances, the study team will continue to track all data at specified time-points and the registered dietitian will re-assess nutritional caloric goals. Moreover, for subjects at lower BMI percentiles, despite the anticipated body fat gain, should the BMI percentile decrease to <5th percentile, the subject will come off-therapy as per Section 12.1.

8.0 SUPPORTIVE CARE GUIDELINES

All supportive care should be provided as per standard of care and institutional guidelines. No specific precautions are required for patients on study.

9.0 REQUIRED OBSERVATIONS

Please see “experimental schema” in study preamble for overview of treatment and required observations.

9.1 REQUIRED OBSERVATIONS

“At Diagnosis” blood samples should be collected before or in closest proximity as possible to starting systemic chemotherapy (steroid pre-treatment, steroid prophylaxis, or intrathecal therapy may have already been given), but all samples must be collected before the start of the activity/nutrition intervention and prior to the end of chemotherapy day 4

The DXA scan should be done in closest proximity to diagnosis as is feasible, but **must be done within 96 hours from the beginning of systemic chemotherapy** and ideally before the start of the activity/nutrition intervention. The timing of the DXA scan in relation to chemotherapy and the intervention will be recorded.

STUDY MEASURE		Diagnosis (Day 1)	Day 8	Day 15	Day 22	End Induction (Day 29)	Start IM#1	Start Maint
Patient History	Clinical History ^{1*}	X	X	X	X	X	X	X
Anthropo-metrics	Height/Weight*	X	X	X	X	X	X	X
	Tricep skin folds	X	X	X	X	X	X	X
	Waist to hip ratio	X	X	X	X	X	X	X
Clinical Assessments	RD Assessment-3 day food log	X				X		
	RD Assessment-24 hr recall	X	X	X	X	X	X	X
	PT Assessment-Complete BOT2	X				X		
	PT Assessment-BOT2 –Brief		X	X	X		X	X
	Fitbit Tracker	Continuous from time of study entry until study end						
Laboratory Tests (blood) ²	Liver function tests ^{3*} (AST/ALT/Bili)	X	X	X	X	X		
	Lipid Panel	X				X	X	X
	[name] Labs	X				X	X	X
	Peripheral blood leukemia blasts ⁴	X						
	Pregnancy Test*	X				X		
Pathology Tests	Bone Marrow Aspirate ^{5*}	X				X		
	Biopsy Marrow Biopsy ⁵	X*				X		

Radiology Tests	DXA Scan	X				X ⁶		
Survey Instruments ⁷	PedsQL - Core	X				X	X	X
	PedsQL - Fatigue	X				X	X	X
	CASP	X				X	X	X

*Indicates test per Standard of Care (SOC). ¹ Clinical History includes any time NPO, any use of nasogastrintestinal (NG) or nasojejunal (NJ) nutrition, any parenteral nutrition, any surgeries, any ICU admissions, Grade 3 or 4 hepatic or pancreatic toxicity, presence of osteonecrosis or fracture. ²Research laboratories to include IGF-1 and obesity-related interleukins/signaling factors, leptin, adiponectin. Peripheral blood will not be collected in patients who are Jehovah Witness or with a medical contraindication. ³ Will record if collected routinely per SOC. Each visit ± 3 days. End of induction includes any time prior to start of Consolidation phase. If Grade 3 hepatic toxicity during induction, will record values with date of resolution through start of IM#1 (<grade 2). ⁴To be collected in those with a circulating absolute blast count $\geq 500/\mu\text{L}$. ⁵Extra aspirate for research will be collected as per below only if sufficient specimen is available; only specimens from bone marrow biopsies processed in saline will be collected for study. ⁶End of induction scan to be done between days 29 and 36 of therapy in as close proximity to day 29 as possible and prior to any subsequent systemic chemotherapy. ⁷Available in Spanish and English; if subject does not speak either, will be administered in an assisted manner using in-person or phone-based medical interpreters.

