2.2 FAT MASS AND ALL

Obesity increases the incidence of many cancer types, and obese cancer patients have a higher risk of mortality from their disease (3). In 2007, a landmark study in the Children's Oncology Group (COG) led by [name] from the Children's Hospital Los Angeles (CHLA) demonstrated in two large cohorts (4,314 and 1,160 patients) that obesity at the time of diagnosis increases risk of relapse in children with National Cancer Institute/Rome High-Risk B-precursor ALL (HR-ALL) by 50% (1), a finding independently confirmed in a different population of children (7) in obese adults (8), and by meta-analysis (2). In a recent study, 36% of children with ALL were overweight or obese at diagnosis (9), while in another cohort 23% of children with HR-ALL continued to be obese throughout therapy (10). In our earlier cohort of adolescent and young adults with HR-ALL treated at CHLA, we found an even higher prevalence of high body fat whereas 48% were overweight or obese at diagnosis. Our data also showed that all individuals – both those lean and those obese- gain a significant amount of adipose tissue during the first month of treatment alone ("induction"). On average, patients gained ~20-30% of fat above their starting body fat percentage. The use of glucocorticoids such as dexamethasone and prednisone during induction therapy likely contribute to this fat gain, as they stimulate adipogenesis and appetite. Predisposition to inactivity due to intensive leukemia treatment combined with steroid-induced dietary derangements are therefore likely moderating factors of this marked gain in body fat. As response to leukemia treatment in the first month of therapy is a key determinant of overall prognosis and risk for relapse, and as obesity and body fat are risks factors for relapse, an intervention aimed at reducing the gain in body fat has potential to improve leukemia therapy efficacy starting from the initial time of diagnosis.

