4.7 STUDY ENROLLMENT

Once all applicable eligibility requirements are met, the patient will be enrolled in the study by the research coordinator.

Timing of Enrollment: Patients will ideally be enrolled prior to starting systemic chemotherapy (not including steroid pre-treatment/steroid prophase) but must be enrolled within 24 hours of starting systemic chemotherapy. Enrollment after 24 hours of starting systemic chemotherapy will be allowed at the discretion of the PI (or delegate) through the end of “chemotherapy day” 4.

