13.2 PRIMARY ENDPOINT EVALUATION

The primary endpoint for efficacy is a reduction in gain of body fat percent (per DXA) from diagnosis to the end of induction. From data on 36 patients from the historical cohort at CHLA with DXA scans pre and post induction, there was a significant average fat gain during induction therapy of 5.5 ± 3.3 percent (mean \pm s.d.), $p < 0.001$. Based on a two-sample (36 historical, 36 present study) two-sided t-test with 5% Type I error, there will be at least 90% power to detect a 2.5 percentage point reduction in change in body fat as a result of intervention (e.g. from gain of 5.5 to a gain of 3.0%). Hence, this study has sufficient power to detect subtle, achievable effects on body fat during induction, and will with certainty detect stabilization of or a decrease in body fat during induction.

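### The primary comparison with historical controls is not protected against differences in DXA timing between the cohorts, and the resulting bias could go either way

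*Combined protocol and SAP*

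**What the plan says.** Section 13.2 defines the endpoint: "The primary endpoint for efficacy is a reduction in gain of body fat percent (per DXA) from diagnosis to the end of induction". The comparison is a two-sided, two-sample t-test of 36 study subjects against 36 historical subjects. The historical change is 5.5 ± 3.3 points and the target reduction is 2.5 points. No adjustment is named for this test; Section 13.3 mentions adjustment only for the MRD analyses.

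On baseline timing, Section 9.1 states a preference, "The DXA scan should be done in closest proximity to diagnosis as is feasible", and a hard limit: it "must be done within 96 hours from the beginning of systemic chemotherapy". Scanning before the diet and activity plan starts is preferred but not required ("ideally before the start of the activity/nutrition intervention"), whereas the blood samples must precede it. Section 9.1 adds: "The timing of the DXA scan in relation to chemotherapy and the intervention will be recorded".

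On steroids, Section 4.7 defines the start of systemic chemotherapy as "not including steroid pre-treatment/steroid prophase". Section 5.1 accepts steroid pre-treatment and sets no maximum duration. Section 2.2 says: "The use of glucocorticoids such as dexamethasone and prednisone during induction therapy likely contribute to this fat gain".

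On end timing, footnote 6 to the Section 9.1 table allows days 29 to 36, as near day 29 as possible and before further systemic chemotherapy.

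Section 13.2 describes the historical scans only as taken before and after induction. It gives no windows and no steroid history before the baseline scan.

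**The concern.** A change score measures gain only between the two scans. If study subjects are scanned later after their first steroid dose than the historical subjects were, more of their early gain falls before baseline. Their measured gain is then smaller for a reason unrelated to the intervention. If their end scans come later, the opposite can happen.

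The comparison is not randomised, so nothing in the design balances timing. A difference is plausible. The controls come from one institution, while Section 13.1 says further sites were added to the study. Section 4.7 lets enrolment run to chemotherapy day 4 at the investigator's discretion. Section 6.2.4 places the baseline scan in the same first hospital days as the start of the intervention.

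At stake is whether a difference in mean change can be attributed to the intervention. As written, the plan does not ensure that the first-steroid date is available to check this.

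**Working it through.** **Inputs.** From Section 13.2: historical mean gain 5.5, SD 3.3, 36 per group, target 2.5 points, two-sided 5%. From Section 9.1: baseline limit 96 hours (4 days), end window days 29 to 36 (up to 7 days late). From Section 3.0: induction taken as 28 days. Assumptions: gain is linear over the 28 days, SD is unchanged, and the average lag relative to controls is 1 to 7 days (the documents give no figure).

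**Step 1: the plan's own power.** SE = 3.3 × √(2/36) = 0.778. Normal approximation: 2.5/0.778 − 1.96 = 1.25, giving 89.5%. Noncentral t with 70 df gives 88.7%. The stated figure of at least 90% is reproduced to within 2 points. The smallest significant difference is 1.55 points.

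**Step 2: daily gain.** 5.5/28 = 0.196 points/day.

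**Step 3: later baseline in the study arm, no true effect.** False difference = lag × 0.196, put through the same t-test.

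| Average lag vs controls | False difference | Share of 2.5 | Two-sided rejection |
|---|---|---|---|
| 0 days | 0 | 0% | 5% |
| 1 day | 0.20 | 8% | 5.7% |
| 4 days | 0.79 | 31% | 16.9% |
| 7 days | 1.38 | 55% | 41.4% |

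The lag here is an average over the whole study arm relative to controls. Under the hard limit, an average of 4 days without pre-treatment would need every study subject scanned at the limit and every control at steroid start. An average of 7 days would need pre-treatment.

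**Step 4: later end scan in the study arm only.** If gain continues at 0.196 points/day, 7 × 0.196 = 1.38 points against the intervention. A true 2.5-point effect then appears as 2.5 − 1.38 = 1.12, and power falls from 88.7% to 29.7%. If gain continues only at the target rate of 3.0/28 = 0.107 points/day, the shift is 0.75 and power is 60.2%.

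**Step 5: both together.** A 4-day late baseline with a 7-day late end scan nets (4 − 7) × 0.196 = −0.59 points, against the intervention.

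**Step 6: sensitivity to the rate.** Section 3.0 gives means of 23.3% and 33.7%, a difference of 10.4 points. At 10.4/28 = 0.371 points/day, a 4-day lag gives 1.49 points (59% of target) and about 47% rejection.

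**Step 7: baseline scan after the intervention has begun.** Any early intervention effect falls before baseline and is lost, which biases towards no effect. The documents give no figure from which to size this.

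**The case against.** The strongest reply is that nothing shows the cohorts differ. Section 3.0 describes the historical change as running from diagnosis to end of induction, the same span as the endpoint. If scan timing was similar, the missed gain cancels and the type I error stays at 5%. That is correct, and it is why no bias can be asserted.

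The protocol also has safeguards. The baseline target is proximity to diagnosis, with 96 hours only the outer limit. The end scan is to be close to day 29, and baseline timing is recorded against chemotherapy and the intervention. These reduce the likely lag. They are preferences rather than limits, and Section 13.2 makes no use of the recorded timing.

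The linear rate is a further weakness. Section 5.1 requires only at least 14 days of glucocorticoid, so gain need not be uniform. The 5.5-point figure itself comes from scans with unknown windows. Nothing shows that a later end scan adds steroid exposure; it adds calendar days. The sizes above are therefore illustrations.

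Two stronger readings are tempting. One is that the scan rules favour the intervention. The documents do not support this: a late baseline favours it only if historical scans came earlier relative to steroid start, while a late end scan (if gain continues) and a baseline after the intervention starts (if it works early) both count against it. The other adds an assumed 7-day prophase to the full 96 hours: 11 × 0.196 = 2.16 points, or 86% of the target. That needs the whole study arm at the extreme and no lag in controls, and no document indicates either.

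**Conclusion.** The concern holds as a gap in protection, not as a demonstrated bias. The hard baseline limit is not tied to first steroid exposure, the historical timing is unstated, and the primary test ignores timing. Under the linear assumption, an average lag of only 1 day has little effect (0.2 points, about 6% rejection). Lags of 4 and 7 days would matter (0.8 and 1.4 points, about 17% and 41%). A 7-day later end scan in the study arm alone could hide more than half of the target effect. Direction and size depend on the timing difference between cohorts, which the documents do not give. The comparison is not invalid on this ground, but as planned it cannot be shown to be free of the problem.

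**What to change.** - **Section 9.1:** also record the date of the first systemic steroid dose, including pre-treatment.
- **Historical cohort:** extract that date and both scan dates for the 36 subjects, and report the timing distributions by cohort.
- **Section 13.2, adjusted analysis:** prespecify an analysis of change adjusted for days from first steroid dose to baseline scan and for the scan-to-scan interval.
- **Section 13.2, sensitivity analysis:** restrict both cohorts to baseline scans within 96 hours of the first steroid dose.
- **Study arm only:** report separately the result excluding baseline scans done after the intervention began. Controls had no intervention, so this filter cannot be applied to both cohorts.

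The cost is one extra date per study subject, chart extraction for 36 controls, and added analysis wording. No scan or visit is added. The sensitivity set will be smaller, and the adjusted estimate will be somewhat less precise if timing is confounded with cohort.

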9.2 RADIOLOGY

For those subjects who are female and of reproductive age, in addition to a pregnancy test at study entry as per routine care prior to chemotherapy, pregnancy will be assessed as per institutional guidelines at each site prior to any radiological tests. The results of these tests will be confidential.

9.3 BONE MARROW ASPIRATE & BIOPSY

As per the preceding CHLA ALL Obesity Environment & Microenvironment Study #2, subjects on study may require extra bone marrow aspirate and biopsy for study purposes. The bone marrow aspirates will be collected during the same anesthesia and procedure being done for clinical care purposes and will be collected after the clinical specimen is obtained. If there is insufficient specimen available, there will be no additional aspirates (needle punctures) performed for study purposes only and no bone marrow leukemia cells will be expected from that time-point for study. If a routine bone marrow biopsy at diagnosis was performed with sufficient extra specimen, a piece will be collected for study purposes. Subjects undergoing bone marrow aspiration at end of induction for clinical purposes will also require a single additional research-only bone marrow biopsy to be performed at the same time. For sites that do not (or cannot) collect bone marrow biopsies in saline, marrow biopsies will not be collected for this study.

Similarly, bone marrow biopsies not collected in saline (for any reason) will not be obtained for this study as it precludes analysis of the marrow fat.

9.4 EXTRA SAMPLE

Any extra blood or bone marrow specimens collected at time of diagnosis or later while on this study, which is not needed for clinical purposes by the laboratory or pathology department may be used for further research purposes. Blood may be used for measurements of other related tests including but not limited to amino acids, cytokines, adipose tissue hormones, and/or collection of viable leukemia cells. Extra bone marrow aspirate/biopsy material may be used for examination, culture and studies to investigate cells type and functions. All testing will be done in the context of further investigating the relationships between bone marrow microenvironment, nutrition, osteoblasts, adipocytes and leukemia.

9.5 LABORATORY INFORMATION

Serum levels of standard lipid panel and all other tests performed per standard of care will be performed by the hospital clinical laboratories. Blasts, marrow adipocytes, and serum collected at CHLA for the assessment of obesity-associated laboratories will be stored at The Saban Research Institute until being batch shipped to [name] laboratory where they will be assayed in a batched manner.

Samples collected from patients enrolled at other sites will be stored at that site and shipped directly to the [name] (i.e. these will not be received at CHLA).

Serum is to be aliquoted in 1ml cryovials and FROZEN at -80C. Serum is to be labeled with (1) Study ID, (2) Date, and (3) Study visit.

Coded samples will be shipped to the laboratory of [name]:

[name]., Ph.D.
David Geffen School of Medicine, UCLA
[name]
[name]

In brief, subjects will have central catheters accessed (if applicable) by heme/onc nursing per routine clinical care. Phlebotomy if necessary will be performed by heme/onc clinical nursing or hospital-based clinical laboratory. Blood draws will be coordinated with routine collection where-ever possible. It is recommended that study bags be provided to nursing prior to study visits that will contain all necessary specimen tubes and instruction regarding volumes to be drawn. Labels and/or instructions will be included regarding specimen distribution and specimen processing. At CHLA, for reference (and if study bags unavailable), please see Appendix I which contains all relevant details.

10.0 RADIOLOGY SAFETY INFORMATION

Radiological studies will expose subjects to small amounts of radiation. Subjects will have quantification of body fat content by DXA. This type of scan is necessary as it provides complementary information and is the "gold standard" method to quantify body fat.

Each DXA examination exposes the subjects to less radiation than a single standard chest x-ray (DXA = ~1/6 a standard chest x-ray). DXA confers a radiation total effective dose equivalent (TEDE) of ~0.5 mREM of radiation per scan. This is a total study exposure of ~1 mREM for subjects (2 DXA scans). The critical organ exposed is the gonads; DXA contributes a total study exposure of 0.24 mREM to gonads in subjects. The total radiation exposure from the DXA scans is minimal and well beneath the 100 mREM upper limit considered to be “minimal risk” by the radiation safety committee.

In common terminology, everyone receives a small amount of unavoidable radiation each year named “background radiation.” Some of this radiation comes from space and some from naturally-occurring radioactive forms of water and minerals. Participation on this research study gives the subject the equivalent of about **1 extra day** of this natural radiation **and is less than that of a single standard chest x-ray.**

